### 5.3 Inclusion of Women and Minorities

Both men and women and members of all races and ethnic groups are eligible for this study.

## 6 TREATMENT PLAN

### 6.1 Dosing and Administration

Treatment will be administered on an outpatient basis. Reported adverse events (AEs) and potential risks are described in **Section 1.8**. Appropriate dose modifications are described in **Section 6.5**.

In this study, a cycle will be defined as 21 days. Dosing for capecitabine will be established based upon actual body weight, with capecitabine being prescribed in oral (PO) tablet forms of 500 mg or 150 mg. The administration will be twice daily for two weeks (the first 2 weeks of each 21 day cycle), followed by a 1 week rest. Capecitabine is to be taken with water, within 30 minutes following a meal. The total daily dose will be calculated with dosing split so that comparable doses are administered, approximately 12 hours apart. The PM dose will be 12 hours (+/- 2 hours) after the AM dose. Doses will be rounded to the nearest 150 or 500 mg tablet increment, but may be rounded down at investigators discretion.

Nintedanib is available in 100 mg and 150 mg capsules, which will be administered twice daily for 21 days (i.e., 1 complete 3-week cycle). Both capecitabine and nintedanib may be taken together, with water, within 30 minutes following a meal. Doses should be separated by approximately 12 hours, with the PM dose being 12 hours (+/- 2 hours) after the AM dose.

Patients will be supplied with medication diaries to assess compliance. If a dose is missed, vomited or otherwise not ingested, it will not be replaced; rather, the patient will wait until the next scheduled dose to resume therapy. In the event that dosing is interrupted mid-cycle, the duration of the cycle will not be extended. Doses missed during the interruption will be captured as omitted rather than delayed.

### 6.2 Cohort Management

#### Phase I

The planned dose levels for Phase I are depicted in **Table 2**.

**Table 2 Available Dose Levels**

| Dose level | Capecitabine a                                 | Nintedanib b |
|------------|---|-------------------------|
| -1         | 1500 mg/m  PO daily
(in two divided doses) | 150 mg PO bid           |
| 1          | 2000 mg/m  PO daily                           | 150 mg PO bid           |

|   |   |               |
|---|---|---------------|
|   | (in two divided doses)                                    |               |
| 2 | 2000 mg/m  PO daily
(in two divided doses) | 200 mg PO bid |

a Capecitabine will be taken only on the first 14 days (followed by 7 days off) of the 21 day cycle.

b Nintedanib will be taken for the complete 21 day cycle.

Dose escalation will proceed in a 3+3 fashion. Standard 3+3 rules will be followed until the maximum tolerated (or administered) dose is found. Initially, 3 patients are enrolled at dose level 1. If no dose limiting toxicities (DLTs) are observed, then 3 new patients are escalated to dose level 2. If  $\geq 2$  DLTs are observed, then 3 new patients are de-escalated to dose level -1. If 1 DLT is observed, then an additional 3 patients are enrolled at dose level 1. In those 6 patients at dose level 1, if  $\leq 1$  DLTs are observed we proceed to dose level 2; otherwise we proceed to dose level -1. The same basic principles are followed until the Phase II recommended dose is identified. Planned dose escalation will proceed according to **Table 3**.

**Table 3 Dose Escalation Scheme**

| Number of Participants with a Dose-Limiting Toxicity at a Given Dose Level    | Escalation Decision Rule  |
|---|---|
| 0 out of 3  | Enter 3 participants at the next dose level.  |
| $\geq 2$  | Dose escalation will be stopped. This dose level will be declared the maximally administered dose (highest dose administered). Three additional participants will be entered at the next lowest dose level if only 3 participants were treated previously at that dose.   |
| 1 out of 3  | Enter at least 3 more participants at this dose level. If 0 of these 3 participants experience a dose-limiting toxicity, proceed to the next dose level. If 1 or more of this group suffer a dose-limiting toxicity, then dose escalation is stopped, and this dose is declared the maximally administered dose. Three additional participants will be entered at the next lowest dose level if only 3 participants were treated previously at that dose. |
| $\leq 1$ out of 6 at highest dose level below the maximally administered dose | This is generally the recommended Phase 2 dose. At least 6 participants must be entered at the recommended Phase 2 dose.  |

The recommended Phase 2 dose will be considered tolerable if DLT(s) are observed in at most 1 of 6 patients completing at least 1 treatment cycle at that dose level. Available toxicity information about these drugs suggests that Dose Level 2 will be the recommended Phase 2 dose, and that 9 patients will be required for the Phase 1. Dose escalation will not proceed beyond dose level 2.

### Phase II

- Nintedanib – treatment will be initiated at the RP2D orally twice daily, administered in a continuous fashion.
- Capecitabine – treatment will be initiated at the RP2D orally twice daily, taken for 14 days, followed by a 7 day break.

As in the Phase I study, therapy will be administered in 3 week cycles. Treatment will continue until progression, undue toxicity or at the physician/patient discretion. The primary endpoint is the PFS rate, defined as the proportion of patients who survive without disease progression (per RECIST criteria) for at least 18 weeks after the start of treatment. The 6 patients in Phase 1 patients treated at the recommended Phase 2 dose will be included in Stage 1 of the Phase 2 study. As of 1/29/16, dose level 2 has been determined to be the RP2D.

### 6.3 Criteria for Retreatment

The following criteria must be met prior to initiation of a cycle of therapy:

- ANC > 1000 / mm^3
- Platelet count > 100,000 / mm^3
- AST and/or ALT CTCAE grade ≤ 5X ULN and bilirubin ≤ ULN
- Any additional non-hematologic toxicity of grade ≥ 3 which is potentially attributable to either drug must have resolved to grade ≤ 1 (or baseline)

If a patient achieves a response or stable disease which is maintained ≥ 6 months and discontinues therapy for a reason other than progressive disease, he/she may be considered for retreatment within 3 months of cessation of therapy. This must be approved by the study PI prior to re-initiation of treatment.

### 6.4 Definition of Dose-Limiting Toxicity

Dose limiting toxicity will be defined as any event which meets the criteria below and occurs within the 1st cycle of therapy (21 days).

The following drug-related adverse events will qualify as DLT if considered drug-related:

- Non-hematologic toxicity ≥ Grade 3 (CTCAE v4) **except:** transient electrolyte abnormality, alopecia, sub-optimally treated nausea, vomiting or diarrhea, and isolated elevation of gamma glutamyl transpeptidase. In particular,
  - Gastrointestinal toxicity (e.g. nausea, vomiting, diarrhoea, abdominal pain) or hypertension ≥ CTCAE Grade 3 despite optimal supportive care/ intervention.
  - Nintedanib (BIBF1120) related liver toxicity except GGT\*\*\* as specified below:
    - AST/ALT > 5x ULN\* independent of bilirubin
    - AST/ALT > 2.5 x ULN\*\* **together with** total bilirubin > 1.5 ULN\*\*

\* corresponding to CTCAE Grade 3 toxicity

\*\* corresponding to CTCAE Grade 2 toxicity

\*\*\* An isolated GGT elevation with no corresponding ALT/AST increase will not be considered as DLT.

- Hematological toxicity
  - CTCAE Grade 4 neutropenia that is uncomplicated (not associated with fever  $\geq 38.5^{\circ}\text{C}$ ) only if continuing for  $> 7$  days
  - CTCAE Grade 4 febrile neutropenia of any duration if associated with fever  $\geq 38.5^{\circ}\text{C}$
  - Platelet decrease to CTCAE Grade 4, or decrease to CTCAE Grade 3 associated with bleeding or requiring transfusions
- Inability to resume nintedanib (BIBF1120) dosing within 14 days of stopping due to treatment related toxicity
- In case adverse events with CTCAE Grade 3/4 were not judged as DLT from a clinical point of view, the Principle Investigator will obtain a confirmation from the individual investigator regarding the appropriateness of the judgment

Dose escalation will proceed within each cohort according to the scheme in **Table 3**.

Participants who do not have a DLT and who do not complete a full cycle of treatment (at least 75% of the prescribed dose of both nintedanib and capecitabine) will be replaced in the study.

Management and dose modifications associated with the above AEs are outlined in **Section 6.5** and **Section 6.5.2**.

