## **12.4 Safety Analysis**

DLTs are the primary endpoint of this study and are used in the estimation of the MTD and the accompanying of the dose escalation decisions. However, no formal analyses of DLTs are planned. Participants who do not have a DLT and who do not complete a full cycle of treatment will be considered non-evaluable for DLT.

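### Section 6.4 does not say how duration-based DLTs are dated against the 21-day window, and Sections 6.4 and 12.4 remove DLT-free patients with incomplete dosing even when the doses were missed because of toxicity

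*Combined protocol and SAP*

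**What the plan says.** **Window.** Section 6.4: "Dose limiting toxicity will be defined as any event which meets the criteria below and occurs within the" first "cycle of therapy (21 days"). Section 6.1 fixes its length: "In the event that dosing is interrupted mid-cycle, the duration of the cycle will not be extended".

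**Duration-based criteria.** Section 6.4 lists "Inability to resume nintedanib (BIBF1120) dosing within 14 days of stopping due to treatment related toxicity" and uncomplicated grade 4 neutropenia only if it lasts more than 7 days. No section says whether these are dated at onset or at completion, or whether follow-up after day 21 can complete them.

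**Replacement and evaluability.** In Section 6.4, participants without a DLT "who do not complete a full cycle of treatment (at least 75% of the prescribed dose of both nintedanib and capecitabine) will be replaced". Section 12.4: "Participants who do not have a DLT and who do not complete a full cycle of treatment will be considered non-evaluable for DLT". Section 12.4 does not repeat the 75% figure. Neither sentence looks at why doses were missed.

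**Holds below the DLT threshold.** Table 4 interrupts both drugs for vomiting of grade 2 or more, and for diarrhoea of grade 2 or more lasting over 7 days, in each case despite optimal supportive care. Table 6 interrupts capecitabine alone for hand-foot syndrome of grade 2 or more. Table 10 holds treatment for other grade 2 events until they improve to grade 1. Missed doses are not made up (Section 6.1: "Doses missed during the interruption will be captured as omitted rather than delayed"), and Section 6.5.1 bars restarting capecitabine in the rest week.

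**Use of the count.** Section 6.2 calls the RP2D tolerable if at most 1 of 6 patients completing at least one cycle has a DLT. It records that dose level 2 was declared the RP2D as of 1/29/16.

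**The concern.** There are two separate problems.

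The first is the dating gap. A failure to restart within 14 days is only established 14 days after the stop. Whether a stop in the second or third week is a DLT then depends on a convention that the protocol does not give.

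The second does not depend on dating. Patients whose doses were held because of drug toxicity, without reaching a DLT, can leave the denominator in the same way as patients who missed doses for unrelated reasons. Removal related to tolerability is informative: the patients left are those who could take the drugs.

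The count matters because Phase II has no formal interim analysis or stopping rule (Sections 4.1.2, 12 and 12.5), so it is the only numerical tolerability criterion before up to 30 further patients are enrolled. The six RP2D patients from Phase I also enter the Phase II analysis (Sections 4.2 and 12.3). If any level 2 patient was replaced after a toxicity hold, those six are partly selected for tolerating treatment.

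**Working it through.** **1. The plan's own figure.** Phase I size (Sections 4.2 and 12.1): 3 at level 1 + 6 at level 2 = 9 expected; 3 levels × 6 = 18 maximum. Both reproduce and are not disputed. Neither leaves room for replaced patients.

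**2. Window.** With the last dose on day d, the 14 days end on day d + 14. This is inside the window if d + 14 ≤ 21, so d ≤ 7. Day 7 gives day 21 (inside); day 8 gives day 22 (outside, if dated at completion). Likewise, neutropenia starting on day 15 has lasted 7 days by day 21, not more than 7.

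**3. The 75% threshold.** Doses per cycle from Section 6.1:

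- Nintedanib: 2 × 21 = 42; 75% = 31.5. Missing 11 leaves 31/42 = 73.8%, which fails. Eleven doses are 5.5 days.
- Capecitabine: 2 × 14 = 28; 75% = 21. Missing 8 leaves 20/28 = 71.4%, which fails. Eight doses are 4 days.

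The sentence requires 75% of both drugs, so failing on either is enough. A hold of this length removes a DLT-free patient even if dosing resumes well within 14 days.

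**4. Non-resuming stops.** Assume full dosing through day d and no restart in the cycle.

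| Last full dosing day | Nintedanib taken | Capecitabine taken | Under 6.4, if dated at completion and not otherwise a DLT |
|---|---|---|---|
| 7 | 14/42 = 33.3% | 14/28 = 50.0% | DLT (14 days end on day 21) |
| 8 | 16/42 = 38.1% | 16/28 = 57.1% | Replaced |
| 15 | 30/42 = 71.4% | 28/28 = 100% | Replaced |
| 16 | 32/42 = 76.2% | 28/28 = 100% | Kept, DLT-free |

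Section 12.4, read alone without the 75% figure, would also make days 16 to 20 non-evaluable.

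**5. Effect on the 1-of-6 rule (illustration).** The documents give no rates, so both inputs are assumptions: p is the rate of DLTs captured as defined, and q is the rate of toxicity-related non-completers without a captured DLT. With r the rate entering the count,

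P(at most 1 of 6) = (1 − r)^6 + 6r(1 − r)^5,

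where r = p + q if these patients are counted as DLTs, p/(1 − q) if they are replaced, and p if they are kept as DLT-free. For p = q = 0.10 with replacement, r = 0.10/0.90 = 0.111, and 0.493 + 0.370 = 0.863.

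| p | q | Counted as DLT | Replaced | Kept DLT-free |
|---|---|---|---|---|
| 0.05 | 0.05 | 0.886 | 0.964 | 0.967 |
| 0.10 | 0.10 | 0.655 | 0.863 | 0.886 |
| 0.20 | 0.05 | 0.534 | 0.630 | 0.655 |
| 0.20 | 0.10 | 0.420 | 0.601 | 0.655 |
| 0.20 | 0.15 | 0.319 | 0.569 | 0.655 |
| 0.20 | 0.20 | 0.233 | 0.534 | 0.655 |

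For 14-day non-resumers, the first column against the other two compares readings of the protocol's own definition. For short grade 2 holds, no reading of Section 6.4 makes the patient a DLT, so the first column only shows how far the rule could move.

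**The case against.** **The 14-day criterion can be met after day 7.** A reader might infer that a later stop can never be a DLT. The text does not establish that. If the event is dated at the stop, a day-8 stop counts. Phase I visits on days 1 and 8 of cycle 2 would allow later follow-up. This stands: the defect is an unstated convention.

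**Not every late stop is replaced.** Correct; step 4 limits replacement to last dosing days 8 to 15. Late grade 4 neutropenia mostly does not lead to replacement either. After day 14 capecitabine is complete, and Table 4 interrupts treatment only after more than 7 days without fever. Replacement would need an earlier hold, for example under Table 10's grade 4 row.

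**The gap is narrow.** Most drug-related non-haematological events of grade 3 or more, the liver criteria, febrile neutropenia and severe thrombocytopenia are DLTs without the 14-day rule. This stands. What remains is mainly persistent grade 2 toxicity and the excepted events.

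**Replacement is not the most lenient option.** Keeping the same patients as DLT-free gives a higher chance of passing (0.655 against 0.569 at p = 0.20, q = 0.15). So a reader should not infer that replacement lowers the DLT rate as defined: p/(1 − q) exceeds p. The contrast of 0.569 with 0.319 needs every such patient to be recounted as a failure.

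**Safeguards exist.** Section 12.4.1 tabulates toxicity for everyone treated. The Phase 1 Committee reviews the study, and Appendix A requires possible-DLT memos and weekly or bi-weekly calls. These keep the events visible but do not put the patients back into the 1-of-6 count.

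**The RP2D is already declared.** Rewording alone changes no remaining escalation decision. This shapes the fix, but the reported Phase I result can still be qualified.

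**Conclusion.** The point holds in two parts. First, Section 6.4 leaves the dating of duration-based DLTs open. If they are dated at completion, nintedanib stops with a last dose after day 7 are missed, by replacement for days 8 to 15 and by staying as DLT-free from day 16. That split assumes full dosing before the stop, no restart in the cycle and no other DLT criterion met.

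Second, and independently, the replacement and evaluability sentences take toxicity-limited patients out of the count once they miss 8 capecitabine or 11 nintedanib doses. This can make the 1-of-6 finding look better than the tolerability actually seen.

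The size cannot be stated. Over the tabulated rates, the chance of passing with replacement exceeds the chance if these patients were counted by between 0.078 (0.964 − 0.886) and 0.301 (0.534 − 0.233). Those rates are assumed, and the contrast is an upper bound on what the rule could hide. The documents do not show that any patient was replaced after a toxicity hold, so they do not support the inference that dose level 2 was wrongly declared tolerable. Nor do they make every patient below 75% a tolerability failure; that would be a new clinical rule.

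**What to change.** 1. In Sections 6.4 and 12.4, reconcile the 21-day window, the two duration-based criteria, the replacement sentence and the evaluability sentence. State how duration-based events are dated and whether follow-up past day 21 completes them. Use one definition of a completed cycle; Section 12.4 now omits the 75% figure. Separate toxicity-related from other reasons for incomplete dosing.
2. List every replaced or non-evaluable Phase I patient with dose level, stop day and reason. If there were none, say so, which largely closes the matter for the declared RP2D. Patients who stopped after day 15 and were kept as DLT-free should be checked against the dating convention as well.
3. Report the Phase I DLT table twice: as defined, and as a sensitivity tabulation with toxicity-related non-completers kept in the denominator and shown as their own category, without relabelling them as DLTs.

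The cost is a wording change and a re-tabulation of 9 to 18 patients plus any replaced. Reported tolerability may look slightly less favourable.

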| Statistical Analysis | 
Sample Size Determination: Sample size determination for the phase I portion will depend upon the dose-toxicity profile, but is expected to be between 9-18 patients. For the phase II portion, with an alpha of 0.1, assessment of 36 patients allows for a power of 0.8 to detect a minimum difference of 17% in the PFS at 18 weeks, assuming a rate of 25% under standard of care.
 
Randomization: No randomization is required.
 
Efficacy Analysis: Primary interest is in the PFS at 18 weeks after enrollment. The PFS at 18 weeks will be described by binomial proportion estimates and 90% confidence intervals. All patients in the phase II study and those treated at the RP2D in the phase I study will be included for analysis.
 
Safety Analysis: Adverse events will be tabulated. AE rates will be described using binomial proportions and 90% confidence intervals.
 
Correlative Data Analysis: Mechanistic PK/PD modeling will be employed, examining the relationship between nintedanib pharmacokinetics, modulation of CAFs and PFS.
 |
|-----------------------------|--|

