#### **Sample Size Justification:**

In Phase I, using the standard 3+3 design, there will be a minimum of 9 and maximum of 18 patients enrolled.

In Phase II, the sample size calculations are based on the primary analysis of the 18-week PFS rate. Historically, the 18-week PFS rate is 5% and 25% for refractory metastatic colorectal cancer patients treated with placebo and regorafenib, respectively. The combination of nintedanib and capecitabine is expected to provide an 18-week PFS of at least 40% in patients with refractory metastatic colorectal cancer. The sample size calculation is based on testing hypotheses concerning the proportion of the treated population alive and progression free 18 weeks after enrollment. Let p represent the proportion of patients surviving with no evidence

of disease progression by RECIST at 18 weeks after start of treatment. A true PFS rate of less than  $p_0 = 0.25$  is considered unacceptable and evidence of such will deem the treatment not worthy of further study, as regorafenib has historically achieved this success rate. The null and alternative hypotheses to be tested are  $H_0: p = p_0$  versus  $H_1: p > p_0$ .

This single-stage design requires a total of 36 evaluable patients to achieve approximately  $1 - \beta$  power to detect a difference of at least  $\Delta$  percentage points ( $p_0$  versus  $p_0 + \Delta$ ). For calculations in this study,  $p_0 = 0.25$ ,  $\alpha = 0.10$ ,  $1 - \beta = 0.80$  and  $\Delta = 0.17$ . With these design parameters, the sample size was calculated using PASS v11.

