### *Primary Analysis:*

The Phase I portion of the study begins by enrolling 3 patients at Dose Level 1 (see **Table 2**). Standard 3+3 rules will be followed until the maximum tolerated (or administered) dose is found. The recommended Phase 2 dose will be considered tolerable if DLT(s) are observed in at most 1 of 6 patients completing at least 2 treatment cycles at that dose level. Available toxicity information about these drugs suggests that Dose Level 2 will be the recommended Phase 2 dose, and that 9 patients will be required for the Phase 1. The 6 Phase 1 patients treated at the recommended Phase 2 dose will be included in Stage 1 of the Phase 2 study.

The Phase 2 study's primary endpoint is the PFS rate, defined as the proportion of patients who survive without disease progression (per RECIST criteria) for least 18-weeks after the start of treatment. Patients who progress or die (due to disease or any cause) prior to 18-weeks will be counted as failures.

The following hypothesis about the true 18-week PFS rate ( $p$ ) will be evaluated using a one-sided exact binomial test:

$$H_0: p = 0.25 \text{ versus } H_1: p > 0.25.$$

If  $T = 12$  or fewer PFS responses are observed among the total  $n_1 + n_2 = 36$  evaluable patients, the therapy will be deemed ineffective; otherwise, it will be concluded that the therapy is promising. The analysis will be conducted in SAS v9.4 (Cary, NC) at a nominal significance level of  $\alpha=0.10$ .

*Secondary Analysis:* In Phase II the secondary outcomes include: overall (OS) and progression free (PFS) survival, and toxicities. A survival event is defined as a patient who experiences death from cancer or any cause, while a patient is considered censored if they are alive at the end of the

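### The plan does not say whether Phase I patients replaced at the RP2D count in the 18-week PFS test; read literally, the body text can drop likely early failures, with a modest favourable bias

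*Combined protocol and SAP*

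**What the plan says.** **Replacement.** Section 6.4: "Participants who do not have a DLT and who do not complete a full cycle of treatment (at least 75% of the prescribed dose". The threshold covers nintedanib as well as capecitabine, and such patients are replaced in the study. Section 12.4 calls patients without a DLT who do not complete a cycle non-evaluable for DLT. It says nothing about PFS.

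**Who enters the primary test.** Section 12.3: "The 6 Phase 1 patients treated at the recommended Phase 2 dose will be included in Stage 1 of the Phase 2 study". Section 6.2 says nearly the same, and 4.2 puts the number carried over at six. The synopsis is worded by treatment received: "All patients in the phase II study and those treated at the RP2D in the phase I study will be included for analysis".

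**Design and decision rule.** Synopsis: "with an alpha of 0.1, assessment of 36 patients allows for a power of 0.8 to detect a minimum difference of 17" percentage points, "assuming a rate of 25% under standard of care". Section 12.1: "This single-stage design requires a total of 36 evaluable patients to achieve approximately" the stated power. 'Evaluable' is not defined for the PFS endpoint. Section 12.3 says that the hypothesis "will be evaluated using a one-sided exact binomial test" at 0.10. It also gives a count: the therapy is ineffective if 12 "or fewer PFS responses are observed among the total" of 36 evaluable patients, and promising otherwise. Progression or death from any cause before 18 weeks is a failure. The synopsis and 4.2 provide for up to 30 further patients, for a Phase II total of 36.

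**The concern.** Replacing a patient who leaves cycle 1 without a DLT is sound for counting DLTs. It should not decide who is in the efficacy analysis. A patient who progresses or dies of disease in cycle 1 without a DLT is a certain failure on the primary endpoint, and is also a patient whom 6.4 replaces.

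The sentence in 12.3 just before the carry-over statement judges the RP2D on six patients completing at least two cycles (6.2 says at least one). A reader can fairly take the six carried forward to be those same six, left after replacement. The synopsis points to the larger set. In a single-arm test no control group absorbs the loss of early failures, so the error can only favour the treatment. The trial is open-label, so an unstated primary set could be settled after outcomes are known.

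There is a smaller, separate gap. If all treated patients are counted and accrual is not adjusted, n exceeds 36, and the plan gives no critical count for any other n.

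**Working it through.** **Inputs from the plan.** Null rate 0.25; difference 0.17, so the alternative is 0.42; one-sided exact binomial test at 0.10; n = 36; promising if 13 or more successes; six patients from Phase I and 30 new ones.

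**Input assumed.** The share d of RP2D patients who stop in cycle 1 without a DLT and are replaced. The documents give no such rate, so a range is shown.

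**Step 1: the plan's own figure.** With X ~ Bin(36, p):
- level = P(X ≥ 13 | p = 0.25) = 0.0922
- power = P(X ≥ 13 | p = 0.42) = 0.811

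The smallest n with exact level at most 0.10 and power at least 0.80 is 36, so the stated design reproduces. The margin below 0.10 is 0.10 − 0.0922 = 0.0078.

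**Step 2: only the six left after replacement are counted.** Suppose every replaced patient would have failed. Under the null, each of the six then has success probability 0.25/(1 − d). The total is Bin(6, 0.25/(1 − d)) + Bin(30, 0.25), and the level is the probability that it reaches 13.

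| d (assumed) | success probability of the six | level |
|---|---|---|
| 0 | 0.250 | 0.0922 |
| 5% | 0.263 | 0.0975 |
| 10% | 0.278 | 0.1037 |
| 15% | 0.294 | 0.1108 |
| 20% | 0.313 | 0.1191 |

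The level reaches 0.10 at d of about 7.1%.

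**Step 3: a milder assumption.** If replaced patients succeed at half the null rate (12.5%, illustrative) and d = 10%, each of the six has probability (0.25 − 0.10 × 0.125)/0.90 = 0.264. The level is then 0.098, still below 0.10.

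**Step 4: n above 36.** With all patients independent at 0.25, P(X ≥ 13) is 0.1109 at n = 37, 0.1317 at 38 and 0.1545 at 39. These figures are not on the same footing as step 2. If the extra patients are all failures they add no successes, and the fixed count of 13 has the step 2 levels instead.

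**Step 5: the two rules in 12.3 at n = 37.** With 13 successes the exact p-value is 0.111, so the test does not reject at 0.10. The count written for 36 would call the same result promising.

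**Step 6: smallest count with exact level at most 0.10, by n.**

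| n | successes needed | level | power at 0.42 |
|---|---|---|---|
| 34 | 13 | 0.0610 | 0.730 |
| 35 | 13 | 0.0756 | 0.773 |
| 36 | 13 | 0.0922 | 0.811 |
| 37 | 14 | 0.0577 | 0.750 |
| 38 | 14 | 0.0710 | 0.790 |
| 39 | 14 | 0.0862 | 0.825 |
| 40 | 15 | 0.0544 | 0.768 |

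**The case against.** The other side has a good deal right.

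- **The text speaks of patients treated.** The carried-over group is described throughout by treatment at the RP2D, six is the number expected from a 3+3 design, and 12.4 limits non-evaluability to DLT. This stands as a reason to prefer the synopsis reading. It does not remove the conflict, because 6.4 replaces patients in the study without qualification and 12.3 fixes the number at six.
- **Type I error need not exceed 0.10.** A reader might infer that either reading must break the stated level. The documents do not support that. The selection reading stays within 0.10 below about 7% loss, even if every leaver fails. Section 12.3 ties the count of 12 to 36 patients and also names an exact test, which protects the level at any other n if it is the rule applied.
- **n need not exceed 36.** A reader might also infer that the only choices are a selected six or too many patients. Because accrual is up to 30 for a total of 36, seven RP2D patients and 29 new ones would fit the text. That stands, although nothing in the plan instructs it.
- **The six are not purely patients who lasted a cycle.** A patient who stops early with a DLT is not replaced. The trigger is dose taken, so a replaced patient could stay on treatment and be progression-free at 18 weeks. This stands and makes step 2 an upper-end calculation.
- **It may never have happened.** Section 6.2 records that dose level 2 was set as the RP2D by 1/29/16, and no replacement there is reported. This stands. The sponsor can settle it from its own records.

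**Conclusion.** The concern holds in a limited form. The replacement rule, the fixed six in the body and the all-treated wording of the synopsis do not define one primary set, and the body reading can remove likely early failures from an uncontrolled primary endpoint. The bias is favourable and modest: at an assumed 10% loss with every replaced patient failing, the level is 0.104 against 0.092 as designed, 0.4 percentage points above the stated 0.10. It is smaller if some replaced patients succeed, and nil if nobody was replaced at dose level 2. The loss rates are assumptions.

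The missing critical count for n other than 36 is a separate, lesser gap. The 0.111 at n = 37 arises only if the count for 36 is used unchanged and all 37 patients are taken as independent at the null rate.

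The point still merits correction because it concerns who is in the primary analysis and is easily settled.

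**What to change.** In 12.3, in line with the synopsis, state that every Phase I patient who received any study drug at dose level 2, including those replaced for DLT counting, is in the 18-week PFS analysis. State also that new Phase II accrual is reduced so that the total stays 36. The level remains 0.0922 and the power 0.811, with no extra patients. Align the wording in 4.2 and 6.2, and say how many patients, if any, were replaced at dose level 2.

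As a fallback only, if the final n is not 36, take the critical count from the exact binomial test for that n: 13 or more for 34 to 36, 14 for 37 to 39, 15 for 40. Report the attained power, because this route has a cost: 0.730 at n = 34, 0.750 at 37 and 0.790 at 38 all fall short of the planned 0.80, while 39 gives 0.825. The whole change is two or three sentences.
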